## **1. STATEMENT OF HYPOTHESIS AND OBJECTIVES:**

Surgical procedures are an essential piece of a dermatologist's practice. In fact, it has been reported that dermatologists perform over 25 million minor surgical procedures annually. A major focus of these procedures is to restore the integrity of the skin while minimizing scarring and potential complications. With dermatologic surgeries being so numerous, there is much discussion about how to optimize post-surgical wound care while decreasing potential barriers to healing. Recent advances in wound therapy have resulted in the development of advanced wound care therapies, such as collagen-based dressings, for use as adjunctive therapies to combat the molecular defects present in wounds.

We have designed a pilot study investigating the efficacy of Nuvagen™ (collagen powder) in treating skin punch biopsy wounds. The objectives of the study are as follows:

Primary objective:

1. To evaluate the effect of Nuvagen™ (collagen powder) on complete wound healing using punch biopsy sites as an acute full-thickness human wound model based on clinical wound closure.
2. To evaluate the effect of Nuvagen™ (collagen powder) on complete wound healing using punch biopsy sites as an acute full-thickness human wound model based on histology of wound site at 4 weeks following injury.

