Additionally, collagen powders have the potential to satisfy many requirements of an ideal adjunctive wound therapy. Collagen is biodegradable, non-toxic, and naturally biocompatible with low antigenicity. Collagen itself promotes thrombosis and hemostasis while having hydrophilic properties useful for absorbing fluid in exuding wounds and maintaining moisture balance. Collagen is also a poor culture medium and can be left in wounds without risk of enhancing bacterial growth. Lastly, collagen powders are easy to apply and are indicated for use in most wound types, including infected wounds.

We have designed a pilot study to investigate the effect and potential utility of topical Nuvagen™ (collagen powder) on the rate and quality of wound healing in healthy volunteers using the punch biopsy method. After inducing an acute full-thickness wound, the rate of complete healing of a wound treated with topical Nuvagen™ (collagen powder) will be compared to the rate of complete healing of a wound treated with primary closure with sutures, the current gold standard. Qualification and semi-quantification of histologic and immunohistochemical markers will be used to assess the maturity and structural stability of the wound bed. Positive findings would suggest that Nuvagen™ (collagen powder) may be capable of stimulating the healing of acute wounds in a similar or even superior manner to primary closure, suggesting collagen powder may be used in place of sutures, and encouraging further studies to characterize its therapeutic potential in dermatologic surgery.

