### 3.4 Treatment Phase

On the first visit, eligibility criteria will be confirmed. Investigators will select 1 area on each anterior, proximal thigh of each volunteer where one 4 mm punch biopsies will be performed. The 2 areas will be cleansed using an alcohol swab, and anesthetized using 1 mL of 2% lidocaine with epinephrine. An Integra Miltex 4.0 mm Standard Biopsy Punch instrument will be used to create 2 full-thickness wounds, one on each thigh on each leg. Hemostasis will be obtained using Aluminum Chloride 20%, application of pressure, and gauze. Each wound will be photographed with a measurement instrument and then cleaned with normal saline prior to treatment. One wound will be selected for treatment with collagen, while the contralateral wound will undergo primary closure with sutures (1-2 epidermal sutures, 4-0 Prolene™ Polypropylene Sutures, Ethicon, Somerville, NJ).

The wound selected for collagen treatment will receive 1 gram of topical Nuvagen™ (collagen powder) directly on the wound with pressure applied using a dry gauze and forceps. Once hemostasis has occurred between 1 and 5 minutes later, the wound will be covered with a sterile dressing. The other wound will undergo primary closure. Both punch biopsy sites will be covered with a non-adherent dressing and a waterproof film dressing.

The patient will be provided with a 2-week supply of Nuvagen™ (collagen powder) in 1-gram containers and dressings along with instructions. Instructions will detail the following procedure: 1) Irrigate the wound with tap water or saline solution, 2) Dry the wound with a dry gauze pad pat using gentle pressure, 3) Apply 1 gram of Nuvagen™ (collagen powder) to the wound, and 4) Apply a sterile dressing which covers the entire wound. Assistance from a caregiver will be permitted in any instance in which this procedure is difficult for the patient to carry out for him or herself. This procedure is to be repeated daily for 2 weeks. On days of study visits, patients will be instructed to bring the day's 1 gram of Nuvagen™ (collagen powder) to the clinic for study coordinators to apply the corresponding day's collagen treatment.

One week after wounding, the patient will return for visit 2. Patients will perform the Patient Overall Assessment Score, wounds will be measured, photographs will be taken, and inquiry will be made about any possible adverse events. The patient's wound treated with collagen will then be treated and dressed in the office.

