One week after visit 2, the patient will return for visit 3. Sutures will be removed, and the wound treated with collagen will be evaluated for further collagen treatment. The principal investigator will determine if another 2 weeks of Nuvagen™ (collagen powder) treatment will be warranted. If further collagen treatment is advised, the patient will be provided with another 2-week supply of Nuvagen™ (collagen powder) and dressings. Patients will perform the Patient Overall Assessment Score, wounds will be measured, photographs will be taken, and inquiry will be made about any possible adverse events. The wound treated with collagen will be treated and dressed in the office.

Two weeks after visit 3, the patient will return for visit 4. Both wound sites will be photographed and then biopsied again following the procedure from visit 1. Each wound will be treated identically (either with primary closure or with collagen powder) as it was in visit one. Patients will be provided with adequate supplies for at-home collagen treatment for 2 weeks. Patients will perform the Patient Overall Assessment Score, wounds will be measured, photographs will be taken, and inquiry will be made about any possible adverse events.

Two weeks after visit 4, the patient will return for visit 5. Sutures will be removed, and the wound treated with Nuvagen™ (collagen powder) will be evaluated for further collagen treatment. The principal investigator will determine if another 2 weeks of Nuvagen™ (collagen powder) treatment will be warranted. If further collagen treatment is advised, the patient will be provided with another 2-week supply of Nuvagen™ (collagen powder) and dressings. Patients will perform the Patient Overall Assessment Score, wounds will be measured, photographs will be taken, and inquiry will be made about any possible adverse events. The wound treated with collagen will be treated and dressed in the office.

Six weeks after visit 5, the patient will return for visit 6. Patients will perform the Patient Overall Assessment Score, wounds will be measured, photographs will be taken, and inquiry will be made about any possible adverse events.

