### **3.6 Strength and Limitations of Proposed Research**

Strengths of the study include its relatively simple design and the potential for its completion within a short period of time due to the small number of participants (eight).

Limitations of this study include the inability to conduct robust statistical analysis due to its small sample size. However, the results of this project may lead to the development of larger studies that will have the statistical power to detect improvements.

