## 4.3 Statistical Considerations

Since this is a pilot study, we will perform only basic descriptive statistical analysis of our results. Due to the small number of subjects, it is unlikely that any statistical test would have the power to detect a significant difference in any of the measured variables. Instead, we will look at

wound closure, quality of forming scar histologically, and assess patient experience and preference. The results of this project may lead to the development of larger studies that will have the statistical power to detect significant differences in these variables after treatment with Nuvagen™ (collagen powder).

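### Section 4.3 commits to no paired estimate or interval for the 8 collagen/suture pairs, while Section 2 says undefined positive findings would suggest healing similar to sutures

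*Combined protocol and SAP*

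**What the plan says.** Section 3.2 sets enrolment at 8 patients. Section 3.4 makes the comparison within-person: "One wound will be selected for treatment with collagen, while the contralateral wound will undergo primary closure with sutures". Section 2 commits to comparing the two sides: complete healing of the collagen wound "will be compared to the rate of complete healing of a wound treated with primary closure with sutures".

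The primary objectives in Section 1 are clinical closure, with no time stated, and healing "based on histology of wound site at 4 weeks following injury". Section 4.2 (Wound specific variables) defines the measurements wound by wound: uncovered area, percentage re-epithelialization, collagen-stained area and CD31-stained area. It defines no contrast between a patient's two wounds.

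The analysis plan in Section 4.3 is brief: "Since this is a pilot study, we will perform only basic descriptive statistical analysis of our results". The reason given is that 8 subjects are too few for a test to have power. The investigators will look instead at closure, histology, and patient experience and preference.

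On interpretation, Section 2 says positive findings would point to a powder that "may be capable of stimulating the healing of acute wounds in a similar or even superior manner to primary closure". The same sentence then draws an inference for practice, "suggesting collagen powder may be used in place of sutures", before it closes with a call for more research. Neither positive findings nor similar is defined, and no margin is given. Section 3.6 lists as a limitation the "inability to conduct robust statistical analysis due to its small sample size".

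**The concern.** The plan promises a comparison within pairs but does not say what will be reported for it. Low power explains leaving out hypothesis tests. It does not explain leaving out paired counts, within-person differences and intervals, which are themselves descriptive and can be computed from 8 pairs.

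The gap matters because of the reading that Section 2 allows. A pilot too small to detect a difference is also too small to show that there is none. Sections 3.6 and 4.3 caution only about failing to detect improvements or differences. Neither cautions against taking no visible difference as similarity. Under the plan as written, 8/8 closed against 8/8 closed could be reported as support for similar healing, with nothing beside it to show how little it excludes.

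Planning the next study is also at stake, and Sections 3.6 and 4.3 give that as the use of the results. A larger paired trial needs the number of discordant pairs and the SD of the within-person differences. Separate summaries for each side do not generally supply either.

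**Working it through.** **Inputs.** n = 8 pairs (Sections 3.2 and 3.4). The documents state no significance level, power, closure rate, SD or margin, so the 8 cannot be reproduced from any formula. The check is therefore of the precision that 8 pairs give. The two-sided 95% level and the 80% power used below are assumptions.

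**1. Closure on one side (exact Clopper-Pearson).**
- 8/8 closed: lower limit 0.025^(1/8) = 0.631, so 63% to 100%.
- 7/8 closed: 47% to 99.7%.

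**2. Paired difference in closure, collagen minus suture (Tango score interval, approximate at n = 8).**
- All pairs agree: the limits reduce to ±z²/(n + z²) = ±3.841/(8 + 3.841) = ±0.324, so about -32 to +32 points.
- One pair discordant, against collagen: about -47 to +24 points.

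**3. How easily agreement arises.** Suppose the sutured side always closes and collagen truly closes in a proportion p. The chance of seeing 8/8 on both sides is then p^8: 0.8^8 = 0.168 and 0.9^8 = 0.430. Both values of p are assumed. If the sutured side can also fail, the joint chance is lower.

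**4. Continuous measures (histology, wound area; approximately normal differences).**
- Half-width of the 95% interval for the mean within-person difference: t(0.975, 7)/√8 = 2.365/2.828 = 0.84 SD of the differences. With 7 complete pairs it is 0.92 SD, and with 6 it is 1.05 SD.
- 95% limits for the SD on 7 degrees of freedom: 0.66 to 2.04 times the estimate. The variance ratio, from the unrounded limits, is (2.035/0.661)² ≈ 9.5. The sample size implied for a later trial is uncertain by that factor.

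**5. The same limit applies to difference and to similarity.**
- A paired t-test with n = 8 has about 23% power for a true difference of 0.5 SD, and reaches 80% only at about 1.16 SD. Section 4.3 is right about low power for moderate effects.
- With a true difference of zero, the chance that the 95% interval excludes a deficit of 0.5 SD is also about 23%. For a deficit of 0.25 SD it is about 9%.
- Pairs needed for 80%, by normal approximation: ((1.960 + 0.842)/0.5)² = 31.4, so 32; ((1.960 + 0.842)/0.25)² = 125.6, so 126. These margins are illustrations; the documents give none.

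**6. Why per-side counts are not enough.** Take 7/8 on each side. If the same patient failed on both sides, there are 0 discordant pairs. If two different patients failed, there are 2. The per-side summary is identical, but the paired evidence is not.

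**The case against.** This is an openly descriptive pilot, and much of the case for leaving it alone is sound. Descriptive-only analysis is acceptable at this size. The small sample is disclosed twice, the statement about low power is correct, and no stated figure is wrong.

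A reader might infer more than the documents support, in four ways.
- *That Section 2 sets a rule under which equal results will be declared similar.* It does not. The sentence is background rationale, worded conditionally, and ends by pointing to further studies.
- *That Section 4.3 rules out paired analysis.* It does not. Basic descriptive analysis can include paired counts and differences, and data are kept by participant ID, so the same team could recover the pairing.
- *That 8 pairs can show nothing.* An extreme result could still be detected: 6 discordant pairs all in one direction give an exact McNemar p of 2 × 0.5^6 = 0.031, although 5 give 0.063.
- *That the lack of an open wound without collagen is part of this defect.* That is a design matter which Section 4.3 cannot repair, and Section 2 deliberately chose suturing as the comparator.

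It is also fair to say that the 8/8 against 8/8 result is hypothetical, and that a long list of intervals with no lead estimate would invite selective reading.

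What remains is that hedging does not define positive findings or similar, and nothing in the plan warns against reading agreement in 8 pairs as similarity. The risk of selective reading is met by naming one lead estimate.

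**Conclusion.** The concern holds in a limited form. The defect is not the absence of a test. It is the absence of any committed paired estimate with its uncertainty, alongside an undefined suggestion of similarity to suturing and of use in place of sutures. With complete agreement in 8 pairs, a true difference of about 32 points in either direction would remain compatible with the data. For continuous measures the uncertainty is ±0.84 SD of the differences.

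These sizes assume 8 complete pairs and a 95% level. The paired closure interval is approximate at this n, and the continuous figures assume roughly normal differences. Paired intervals would show the uncertainty but would not make 8 pairs enough to establish similarity. The change is worth making because it alters what the report can fairly conclude.

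**What to change.** **Section 4.3**
- Name one lead closure estimate in the first wounding episode, with complete closure defined in advance. Week 4 before re-biopsy is one candidate, since Section 1 gives closure no time and at visit 4 "Both wound sites will be photographed and then biopsied again following the procedure from visit 1". Table 1 already schedules photographs immediately before that biopsy.
- Report it as a paired 2×2 table with a 95% interval for the paired difference.
- Report the week 4 histology measures as within-person collagen-minus-suture differences with 95% interval and SD, noting that an SD from 8 pairs is imprecise.
- Label all other summaries, including second-episode wound areas and patient preference, as exploratory, with no claims drawn from individual intervals.

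**Section 2**
- State that results are estimates for planning a larger study.
- State that absence of an observed difference in 8 pairs will not be read as similarity or as support for replacing sutures.

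**Cost.** A few lines of analysis and wording, with no extra data or visits. The intervals will be wide and the stated conclusion less favourable to the product.

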## **5. HUMAN SUBJECTS PROTECTION**

### **5.1 Subject Selection**

At the time of recruitment, each potential subject will be provided with an informed consent form to read. The potential subject will be allowed to take the consent form home to discuss its content with family members or friends. All individuals will be given a contact number that they may call to obtain answers to any questions regarding the study and their participation. All subjects must sign a consent form prior to any study procedures being performed.

Involvement of special subjects such as pregnant women, institutionalized individuals, prisoners, or impaired and non-competent individuals are not anticipated in this study. Eligible women of reproductive age will be required to be on 1 reliable form of effective birth control during the treatment period. They will also be required to have a negative urine pregnancy test during the screening period and prior to each treatment session for the duration of the study. Individuals from all racial/ethnic groups, regardless of gender, and those that are economically and educationally disadvantaged are eligible for this study if they meet the eligibility requirements.

### **5.2 Risks and Benefits**

Risks from punch biopsies include the possibility of pain, bleeding, itching, or infection at the biopsy site. Further, there is the possibility of persistent bruising, swelling, or scarring. Pain at the biopsy site will be minimized by use of a local anesthetizing agent. Excessive bleeding will be prevented by excluding patients with known coagulation disorders, patients taking aspirin, or patients taking anticoagulants (including heparin, low molecular weight heparin, warfarin, fondaparinux, or rivaroxaban). Further, bleeding will be minimized by applying adequate pressure using gauze on the biopsy sites. Previous work has shown that wound infections can occur in about 1 in every 6 outpatient skin biopsies. This study failed to subcategorize infection rate for each biopsy type, however, and included patients with medical co-morbidities which contribute to poor wound healing and development of infections. Risk of infection in our study will be minimized by excluding smokers, patients with diabetes mellitus, and patients with other medical or skin conditions that impair wound healing. Collagen is also a poor culture medium and can be left in wounds without risk of enhancing bacterial growth.

Patients may have an allergy or allergic reaction to the numbing agent used, but every attempt to prevent this will be made by asking the patient about his or her allergy history. Furthermore, there is a potential risk of allergy to the interventional type I Nuvagen™ (collagen powder). Although studies have shown that it is possible to develop monoclonal antibodies to mammalian collagen, type I collagen has shown to be very poorly immunogenic. Nonetheless, there have been sparse reports of allergy to topical bovine-derived collagen. Minor amounts of non-collagen proteins in collagen products have also been implicated in immunogenicity of collagen

products. Risk of allergy to the investigational agent used will be minimized further by excluding patients with history of known allergy or sensitivity to any component of the test medication (including bovine and/or collagen products).

There is a potential risk of loss of privacy. All possible precautions will be taken to respect privacy and the confidentiality of patient information, and a secured database with coded identifiers will be used to keep privacy breach risk minimal.

There is no guarantee of direct benefit from study involvement. Information from this study will be used to improve wound care practices after skin biopsies. Subjects could receive up to \$590.00 total for participation if all study visits are attended. For each biopsy procedure, subjects will be compensated \$125.00, for a total of \$500.00 for all 4 planned biopsies obtained during the study (2 biopsies in visit 1, and 2 more biopsies in visit 4). In addition, subjects will be reimbursed \$15.00 for travel expenses for each visit, for a total of \$90.00 for all 6 planned study visits. Subjects will only receive payment for study visits attended and biopsy procedures already performed should he or she decide to stop the study early. Payments are to be made in full to the subject within 2 months after the final visit for the study.

### **5.3 Confidentiality**

All information collected as part of this study will be treated as confidential. Subject consent forms and data collection sheets will be stored in a locked office in the MFA Dermatology Department. These documents will be accessible to study investigators only. A computer database will be created. This database will not contain any subject identifiers. The data within the database will be labeled with each subject's study identification number. Database information will be maintained in a password-protected file. All the data included in this study will only be accessible to the investigators listed on the title page, and they will not be released for use by other researchers.

### **5.4 Adverse Events and Safety Monitoring**

Patients will be closely monitored for any adverse events experienced during this study, as described in Section 5.2: Risks and Benefits. Adverse events monitoring will be performed by the principal investigator during each treatment session starting at visit 2. Any event occurring more than 8 weeks after the second pair of punch biopsies at visit 4 will not be considered an adverse event. Patients will be educated as to the possible side effects and complications related to punch biopsies and Nuvagen™ (collagen powder), and will be instructed to notify any investigator should they experience signs or symptoms of an adverse event. Because the anticipated risks associated with this study are low, we feel that an independent monitoring board will not be necessary.

All events that meet the Prompt Reporting Requirements (HRP-801) (including but not limited to new or increased risk, harm experienced by the subject, noncompliance with the federal regulations governing human research, and state medical board actions) will be reported to the GW OHR via a Problem Report and Promptly Reportable Information Form (HRP-204) within 5 business days of knowledge of the event.

